## **9.11 Visit windows and missed visits**

Visit windows are defined in HVTN 114 Study Specific Procedures. For a visit not performed within the window period, a Missed Visit form is completed. If the missed visit is one that required safety assessments or local safety labs, HVTN CRS staff should attempt to bring the participant in for an interim visit as soon as possible.

Procedures performed at an interim visit are usually toxicity/safety assessments (including local safety labs) and HIV testing. With the exception of HIV testing, these procedures are performed only if they were required at the missed visit or if clinically indicated. HIV testing may be performed as deemed appropriate by the study staff. Blood samples for immunogenicity assays are not typically collected at interim visits.

If a missed visit required vaccination, please see Section 7.3.2 and Section 7.3.3 for resolution.

## **9.12 Early termination visit**

In the event of early participant termination, site staff should consider if the following assessments are appropriate: a final physical examination, clinical laboratory tests (including urine dipstick, CBC with differential, platelet count, and chemistry panel), pregnancy testing, social impact assessment, and HIV test.

## **9.13 Pregnancy**

If a participant becomes pregnant during the course of the study, no more injections of study product will be given, but remaining visits and study procedures should be completed unless medically contraindicated or applicable regulations require termination from the study. In case of required termination, enrollment in an observational study should be offered to the participant. If the participant terminates from the study prior to the pregnancy outcome, the site should make every effort to keep in touch with the participant in order to ascertain the pregnancy outcome.

## **10 Laboratory**

### **10.1 HVTN CRS laboratory procedures**

The HVTN Site Lab Reference Manual provides further guidelines for operational issues concerning the clinical and processing laboratories. The manual includes guidelines for general specimen collection, special considerations for phlebotomy, specimen labeling, whole blood processing, HIV screening/diagnostic testing, and general screening and safety testing.

Tube types for blood collection are specified in Appendix F. For tests performed locally, the local lab may assign appropriate tube types.

In specific situations, the blood collection tubes may be redirected to another laboratory or may require study-specific processing techniques. In these cases, laboratory special instructions will be posted on the protocol-specific section of the HVTN website.

### **10.2 Total blood volume**

Required blood volumes per visit are shown in Appendix F. Not shown is any additional blood volume that would be required if a safety lab needs to be repeated, or if a serum pregnancy test needs to be performed. The additional blood volume would likely be minimal. The total blood volume drawn for each participant will not exceed 500 mL in any 56-day (8-week) period.

### **10.3 Primary immunogenicity timepoints**

The primary immunogenicity timepoints in this study are at visits 4 (day 14) (ie, 2 weeks after the first vaccination visit) and 7 (day 126) (ie, 2 weeks after the second vaccination visit). Endpoint assays for humoral and cellular responses are performed on participants at the primary immunogenicity timepoints and will also be performed at baseline. Depending on the number of responders observed, assays for humoral and cellular responses may be performed on participants at other timepoints; the schedule is shown in Appendix F.

### **10.4 Endpoint assays: cellular**

#### **10.4.1 Flow cytometry**

Flow cytometry will be used to examine vaccine-specific CD4+ and CD8+ T-cell responses following stimulation of PBMCs with synthetic HIV peptides that span the proteins encoded by the vaccine construct. ICS parameters will include cytokines such as IFN- $\gamma$ , IL-2, and TNF- $\alpha$ , and may include other cytokines to identify T cells of specific functionality (such as Th2 and Th17). Markers of cytotoxic potential (Granzyme B, perforin and CD57) may also be included. Data will be reported as percentages of CD4+

or CD8+ T cells responding to a specific peptide pool. Additional cell surface markers, cytokines, or functional markers may also be analyzed.

Flow cytometry will also be used to phenotypically characterize peripheral follicular helper T cells (pTfh). Identification of pTfh will be based on expression of CXCR5 and PD-1 on CD4+ T cells, and may include additional markers.

## **10.5 Endpoint assays: humoral**

### **10.5.1 HIV-1 multiplex Ab assay**

Total binding IgG (IgG1, IgG2, IgG3, IgG4) and IgA Ab to clade B and AE isolates will be assessed on serum samples from study participants taken at the primary immunogenicity timepoints and baseline. This includes Env-specific Ab responses for gp120, gp41, V1/V2, V3, and the IDR of gp41. Specimens from other timepoints as well as other HIV antigens may also be assayed based on the results of the initial assay.

### **10.5.2 Neutralizing Ab assay**

HIV-1–specific neutralizing Ab assays will be performed on serum samples from all study participants taken at baseline and at the primary immunogenicity timepoints. Specimens from other timepoints may also be analyzed at the discretion of the HVTN Laboratory Program, which may be contingent on the results of the primary immunogenicity timepoints. Assays will be performed with the vaccine strain and heterologous strains of HIV-1 that exhibit tier 1 (highly sensitive) and tier 2 (moderately sensitive) neutralization phenotypes [39].

## **10.6 Lab assay algorithm**

The Lab Assay Algorithm lists assays to characterize cellular, humoral, and innate immune responses as well as host genetics that may be conducted to determine endpoints in HVTN vaccine trials. The type of assay(s) employed will be dependent on the response obtained by the primary immunogenicity assays at relevant timepoints. Please note that the Lab Assay Algorithm will be updated periodically to include new assays.

## **10.7 Mucosal studies**

As an exploratory analysis, cervicovaginal secretions, rectal secretions, and semen samples will be collected at timepoints indicated in Appendix F, then processed and assessed for HIV-specific IgA and IgG. Additional exploratory humoral and/or cellular assays may be performed on these samples.

## **10.8 Exploratory studies**

As an exploratory analysis, blood samples will be collected at timepoints indicated in Appendix F, then processed and assessed for ADCC responses and antibody avidity of

Env-specific Ab for V2, V3, and IDR of gp41. Additional humoral assays may be performed on these samples.

Samples may be used for other testing and research related to furthering the understanding of HIV immunology or vaccines. In addition, cryopreserved samples may be used to perform additional assays to support standardization and validation of existing or newly developed methods.

## **10.9 Other use of stored specimens**

The HVTN stores specimens from all study participants indefinitely, unless a participant requests that specimens be destroyed or if required by IRB/EC, or RE.

Other use of specimens is defined as studies not described in the protocol.

This research may relate to HIV, vaccines, the immune system, and other diseases. This could include limited genetic testing and, potentially, genome-wide studies. This research is done only to the extent authorized in each study site's informed consent form, or as otherwise authorized under applicable law. Other testing on specimens will occur only after review and approval by the HVTN, the IRB/EC of the researcher requesting the specimens, and the CRS's IRBs/ECs if required.

The protocol sample informed consent form is written so that the participant either explicitly allows or does not allow their samples to be used in other research when they sign the form. Participants who initially agree to other use of their samples may rescind their approval once they enter the study; such participants will remain in this study and their samples will only be used for the studies described in this protocol. If a participant decides against allowing other research using his or her samples, or at any time rescinds prior approval for such other use, the study site investigator or designee must notify HVTN Regulatory Affairs in writing. In either case, HVTN Regulatory Affairs directs the HVTN Lab Program not to use samples from these participants for such other uses.

CRSs must notify HVTN Regulatory Affairs if institutional or local governmental requirements pose a conflict with or impose restrictions on other use of specimens.

## **10.10 Biohazard containment**

As the transmission of HIV and other blood-borne pathogens can occur through contact with contaminated needles, blood, and blood products, appropriate precautions will be employed by all personnel in the drawing of blood and shipping and handling of all specimens for this study, as currently recommended by the CDC and the NIH or other applicable agencies.

All dangerous goods materials, including Biological Substances, Category A or Category B, must be transported according to instructions detailed in the International Air Transport Association Dangerous Goods Regulations.

## **11 Safety monitoring and safety review**

### **11.1 Safety monitoring and oversight**

#### **11.1.1 HVTN 114 PSRT**

The HVTN 114 PSRT is composed of the following members:

- DAIDS medical officer representative,
- Protocol chair and cochair,
- Protocol Team leader,
- Core medical monitor, and
- Clinical safety specialist.

The clinician members of HVTN 114 PSRT are responsible for decisions related to participant safety.

The Protocol Team clinic coordinator, project manager, vaccine developer representative, clinical trial manager, and others may also be included in HVTN 114 PSRT meetings.

#### **11.1.2 HVTN SMB**

The SMB is a multidisciplinary group consisting of biostatisticians, clinicians, and experts in HIV vaccine research that, collectively, has experience in the conduct and monitoring of vaccine trials. Members of the SMB are not directly affiliated with the protocols under review.

The SMB reviews safety data, unblinded as to treatment arm, approximately every 4 months during the main study, as defined in Section 3 (for safety reviews during the annual health contact period, please see Section 11.4.3). The reviews consist of evaluation of cumulative reactogenicity events, AE, laboratory safety data, and individual reports of adverse events requiring expedited reporting to DAIDS. To increase the sensitivity for detecting potential safety problems, the SMB will review safety data aggregated across multiple protocols that use the same or similar vaccine candidates. The SMB conducts additional special reviews at the request of the HVTN 114 PSRT.

Study sites will receive SMB summary minutes and are responsible for forwarding them to their IRB/EC and any applicable RE.

#### **11.1.3 SDMC roles and responsibilities in safety monitoring**

The roles and responsibilities of the SDMC in relation to safety monitoring include:

- Maintaining a central database management system for HVTN clinical data;

- Providing reports of clinical data to appropriate groups such as the HVTN 114 PSRT and HVTN SMB (Section 11.1.2);

#### **11.1.4 HVTN Core roles and responsibilities in safety monitoring**

- Daily monitoring of clinical data for events that meet the safety pause and HVTN 114 PSRT AE review criteria (Section 11.3);
- Notifying HVTN CRSs and other groups when safety pauses or planned holds are instituted and lifted (Section 11.3);
- Querying HVTN CRSs for additional information regarding reported clinical data; and
- Providing support to the HVTN 114 PSRT.

## **11.2 Safety reporting**

### **11.2.1 Submission of safety forms to SDMC**

Sites must submit all safety forms (eg, reactogenicity, adverse experience, urinalysis, local lab results, concomitant medications) before the end of the next business day after receiving the information. The forms should not be held in anticipation of additional information at a later date. If additional information is received at a later date, the forms should be updated and resubmitted before the end of the next business day after receiving the new information.

### **11.2.2 AE reporting**

An AE is any untoward medical occurrence in a clinical investigation participant administered a study product/procedure(s) and which does not necessarily have a causal relationship with this treatment. An AE can therefore be any unfavorable and unintended sign (including an abnormal laboratory finding), symptom, or disease temporally associated with the use of an investigational study product/procedure(s), whether or not related to the investigational study product/procedure(s). All AEs are graded according to the Division of AIDS Table for Grading the Severity of Adult and Pediatric Adverse Events (DAIDS AE Grading Table), Version 2.0 [November 2014], available on the RSC website at <http://rsc.tech-res.com/safetyandpharmacovigilance/gradingtables.aspx>, except:

- Weight loss is required to be reported as an adverse event only if it is considered to be deleterious to the participant's health (HVTN 114 SSP)
- Sinus arrhythmia will not be reported as an AE;
- PR interval  $\leq$  0.219 sec will not be reported as an AE. The definition of a Grade 1 mild prolonged PR interval (Adult > 16 years) that will be used is 0.22 sec - 0.25 sec;

- Injection Site Erythema or Redness and Injection Site Induration or Swelling will not consider interference with usual social and functional activities such that:
  - Grade 1 is: 2.5 to < 5 cm in diameter OR 6.25 to < 25 cm^2 surface area;
  - Grade 2 is: ≥ 5 to < 10 cm in diameter OR ≥ 25 to < 100 cm^2 surface area;
  - Grade 3 is: ≥ 10 cm in diameter OR ≥ 100 cm^2 surface area OR Ulceration OR Secondary infection OR Phlebitis OR Sterile abscess OR Drainage;
  - Grade 4 is: Potentially life-threatening consequences (eg, abscess, exfoliative dermatitis, necrosis involving dermis or deeper tissue).
- The grading of Insomnia events will consider the criteria within the Insomnia parameter as well as the general AE functional table such that:
  - Grade 1 Insomnia is defined as: Mild difficulty falling asleep, staying asleep, or waking up early causing no or minimal interference with usual social and functional activities with intervention not indicated;
  - Grade 2 Insomnia is defined as: Moderate difficulty falling asleep, staying asleep, or waking up early, causing greater than minimal interference with usual social and functional activities with intervention indicated;
  - Grade 3 Insomnia is defined as: Severe difficulty falling asleep, staying asleep, or waking up early, causing inability to perform usual social and functional activities with intervention or hospitalization indicated.

If a definition of insomnia falls between 2 grades, the final grading will be selected based on the degree of interference with usual social and functional activities caused by the symptoms.

All AEs are reported to the SDMC on the appropriate CRF. Clinic staff should evaluate every AE to determine if (1) the AE meets the requirements for expedited reporting to DAIDS (Section 11.2.3) and (2) if the AE meets the criteria for a safety pause/prompt AE review (Section 11.3).

Sites are expected to notify the Clinical safety specialist of any serious safety concern requiring their attention (Table 11-1). Telephone numbers and email addresses are found on the protocol home page on the HVTN Members' site (<https://members.hvtn.org/protocols/hvtn114>). Concerns requiring immediate attention should be communicated by calling the clinical safety phone.

In the case of email notification, the Clinical safety specialist will reply during working hours (US Pacific Time) to confirm that the email has been received and reviewed. If email service is not available, the HVTN CRS should notify the Clinical safety specialist of the event by telephone, then submit CRFs.

In addition, site investigators are required to submit AE information in accordance with IRB/EC and any applicable RE requirements.

### 11.2.3 Expedited reporting of adverse events to DAIDS

Requirements, definitions and methods for expedited reporting of AEs are outlined in Version 2.0 (January 2010) of the *Manual for Expedited Reporting of Adverse Events to DAIDS* (DAIDS EAE Manual), which is available on the RSC website at <http://rsc.tech-res.com/safetyandpharmacovigilance/>. The SAE Reporting Category will be used for this study.

The internet-based DAIDS Adverse Experience Reporting System (DAERS) must be used for expedited AE reporting to DAIDS. In the event of system outages or technical difficulties, expedited AE reports may be submitted via the DAIDS EAE Form. For questions about DAERS, please contact [[contact]](mailto:[contact]) or from within the DAERS application itself.

Sites where DAERS has not been implemented will submit expedited AE reports by documenting the information on the current DAIDS EAE Form. This form is available on the RSC website: <http://rsc.tech-res.com/safetyandpharmacovigilance/>. For questions about expedited AE reporting, please contact the RSC ([[contact]](mailto:[contact])).

The study products for which expedited reporting are required are:

- MVA/HIV62B and control for MVA/HIV62B
- AIDSVAX B/E and control for AIDSVAX B/E

In addition to the expedited Reporting Category identified above, other AEs that must be reported in an expedited manner are: all myopericarditis events.

While the participant is in the main study reporting period (Section 3), the SAE Reporting Category will be used.

If the participant has completed the main study and is in the “annual health contact reporting period” (Section 3) the SUSAR Reporting Category will be used. In addition, per Section 9.5, all adverse events that are serious are collected on the LTFU Event Log and reported to the SDMC.

After the participant has completed the annual health contact period and is off study, sites must report SUSARS if the study site staff becomes aware of the events on a passive basis (eg, from publicly available information).

The NIAID/DAIDS will report all unexpected SAEs related to the study products observed in this clinical trial to the FDA in accordance with 21 CFR 312.32 (IND Safety Reports). However, because safety is a primary study endpoint, the Sponsor Medical Officer will not be unblinded to study treatment assignment when there is an assessment of relatedness of the SAE with the study product(s); and the safety report will be sent to the FDA based on the blinded attribution assessment.

If the PSRT believes unblinding of the site principal investigator to treatment assignment will assist with the clinical management of the SAE, the PSRT will consult the independent HVTN SMB for a recommendation. In the event the HVTN SMB determines that unblinding is indicated, the SMB will inform the site physician of the participant's treatment assignment in such a manner as to maintain the study blind of the PSRT and study team. For additional impact and management of SAEs on the study, refer to Section 11.3.

#### 11.2.4 Expedited reporting of AEs to pertinent national and local regulatory authorities

Site IoRs/designees outside of the United States will file expedited reports to appropriate national regulatory authorities in accordance with their requirements and EAE information and any other relevant safety information to their ECs/IRBs in accordance with EC/IRB requirements.

### 11.3 Safety pause and prompt PSRT AE review

When a trial is placed on safety pause, all enrollment and vaccinations will be held until further notice. The AEs that will lead to a safety pause or prompt HVTN 114 PSRT AE review are summarized in Table 11-1. Vaccinations may be suspended for safety concerns other than those described in the table, or before pause rules are met, if, in the judgment of the HVTN 114 PSRT, participant safety may be threatened. Criteria for an individual participant's departure from the schedule of vaccinations are listed in Section 7.3.

**Table 11-1 AE notification and safety pause/AE review rules**

| Event and relationship to study products | Severity           | HVTN CRS action a                          | HVTN Core action                                 |
|--|--------------------|---|--|
| SAE, related                             | Grade 5 or Grade 4 | Phone immediately, email and submit forms immediately | Immediate pause                                  |
| SAE, not related                         | Grade 5            | Phone immediately, email and submit forms immediately | Immediate HVTN 114 PSRT notification             |
| SAE, related                             | Grade 3            | Email and submit forms immediately                    | Prompt HVTN 114 PSRT AE review to consider pause |
| AE b , related                | Grade 4 or 3       | Email and submit forms immediately                    | Prompt HVTN 114 PSRT AE review to consider pause |

a Phone numbers and email addresses are found on the Protocol home page on the HVTN Members' site (<https://members.hvtn.org/protocols/hvtn114>).

b Does not include subjective reactogenicity symptoms (injection site pain, tenderness, fatigue/malaise, myalgia, arthralgia, chills, headache, nausea).

For all safety pauses, HVTN Core notifies the HVTN 114 PSRT, HVTN Regulatory Affairs, DAIDS Pharmaceutical Affairs Branch (PAB), DAIDS Regulatory Affairs Branch (RAB), DAIDS Safety and Pharmacovigilance Team (SPT), and participating HVTN CRSs. When an immediate safety pause is triggered, HVTN Core notifies the SMB.

Once a trial is paused, the HVTN 114 PSRT reviews safety data and decides whether the pause can be lifted or permanent discontinuation of vaccination is appropriate, consulting the SMB if necessary. HVTN Core notifies the participating HVTN CRSs, HVTN Regulatory Affairs, DAIDS PAB, DAIDS RAB, and DAIDS SPT of the decision regarding resumption or discontinuation of study vaccinations. Based on the HVTN 114 PSRT assessment, DAIDS RAB notifies the FDA as needed.

If an immediate HVTN 114 PSRT notification or prompt HVTN 114 PSRT AE review is triggered, HVTN Core notifies the HVTN 114 PSRT as soon as possible during working hours (US Pacific Time)—or, if the information was received during off hours, by the morning of the next work day. If a prompt HVTN 114 PSRT AE review cannot be completed within 72 hours of notification (excluding weekends and US federal holidays), an automatic safety pause occurs.

The HVTN requires that each CRS submit to its IRB/EC protocol-related safety information (such as IND safety reports, notification of vaccine holds due to the pause rules, and notification of other unplanned safety pauses). CRSs must also follow all applicable RE reporting requirements.

In addition, all other AEs are reviewed routinely by the HVTN 114 PSRT (Section 11.4.2).

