### **7.3.3 Discontinuing vaccination for a participant**

Under certain circumstances, an individual participant's vaccinations will be permanently discontinued. Specific events that will result in stopping a participant's vaccination schedule include:

- Co-enrollment in a study with an investigational research agent (rare exceptions allowing for the continuation of vaccinations may be granted with the unanimous consent of the HVTN 114 PSRT).
- Clinically significant condition (ie, a condition that affects the immune system or for which continued vaccinations and/or blood draws may pose additional risk), including but not limited to the following:
  - Pregnancy (regardless of outcome);
  - Any grade 4 local or systemic reactogenicity symptom, lab abnormality, or AE that is subsequently considered to be related to vaccination;
  - Any grade 3 lab abnormality or other clinical AE (exception: fever or vomiting and subjective local and systemic symptoms) that is subsequently considered to be related to vaccination; or
  - Clinically significant type 1 hypersensitivity reaction associated with study vaccination. Consultation with the HVTN 114 PSRT is required prior to subsequent vaccinations following any type 1 hypersensitivity reaction associated with study vaccination; or
- Investigator determination in consultation with Protocol Team leadership (eg, for repeated nonadherence to study staff instructions).

Such participants should be counseled on the importance of continuing with the study and strongly encouraged to participate in follow-up visits and protocol-related procedures per the protocol for the remainder of the trial, unless medically contraindicated.

In addition, vaccinations will be stopped for participants diagnosed with HIV infection. HIV-infected participants will not continue in the trial (Sections 7.3.4 and 9.7.1).

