## 9.10 Assessments of reactogenicity

For all participants, baseline assessments are performed before and reactogenicity assessments are performed after each vaccination. All reactogenicity symptoms are graded according to the Division of AIDS Table for Grading the Severity of Adult and Pediatric Adverse Events (DAIDS AE Grading Table), Version 2.0 [November 2014], except as noted in Section 11.2.2).

The reactogenicity assessment period is 3 full days following each vaccination per the assessment schedule shown in Table 9-1. Participants are instructed to record symptoms using a postvaccination symptom log and to contact the site daily during the assessment period. Clinic staff will follow new or unresolved reactogenicity symptoms present at day 3 to resolution. Participants are instructed to contact the clinic for events that arise during the period between vaccination and the next scheduled visit. In general, a participant who self-reports any postvaccination reaction greater than mild is seen by a clinician within 48 hours after onset, unless the reaction is improving and/or has completely resolved.

Reactogenicity events are reported using CRFs that correspond to the time of assessment in Table 9-1. Reactogenicity assessments include assessments of systemic and local symptoms, vaccine-related lesions, and lymph nodes. Events not listed on a CRF, or with an onset after the reactogenicity assessment period (day of vaccination and 3 full days after), or those meeting SAE/adverse events requiring expedited reporting to DAIDS criteria, are recorded on an adverse experience log form.

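### Footnote b of Table 11-1 exempts subjective symptoms from prompt safety review even at Grade 4, where Section 7.3.3 ends the participant's dosing

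*Combined protocol and SAP*

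**What the plan says.** All references are to the combined protocol and SAP.

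**Trial level (Section 11.3, Table 11-1).** One row covers related adverse events of Grade 3 and Grade 4 together. It requires immediate email and forms from the site, and prompt PSRT review to consider a pause. If that review is not finished within 72 hours of notification, weekends and US federal holidays aside, the trial pauses automatically. Footnote b is attached to this row: "Does not include subjective reactogenicity symptoms (injection site pain, tenderness, fatigue/malaise, myalgia, arthralgia, chills, headache, nausea". It names no grade. It is not attached to the rows for serious adverse events (SAEs): a related Grade 4 or 5 SAE causes an immediate pause, and a related Grade 3 SAE goes to prompt review.

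**Individual level (Section 7.3.3).** Here the grades are treated separately. Vaccination stops permanently for "Any grade 4 local or systemic reactogenicity symptom, lab abnormality, or AE that is subsequently considered to be related to vaccination", with no exception. The Grade 3 bullet is the only one with an exception: "Any grade 3 lab abnormality or other clinical AE (exception: fever or vomiting and subjective local and systemic symptoms".

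**How the two relate.** Section 11.3 keeps them apart: "Criteria for an individual participant's departure from the schedule of vaccinations are listed in Section 7.3". It also gives the PSRT discretion: "Vaccinations may be suspended for safety concerns other than those described in the table, or before pause rules are met".

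**The concern.** The protocol treats a related Grade 4 subjective reaction as grave enough to end one participant's dosing. Yet it does not require the body that decides whether everyone else should continue to hear of it promptly. Under the same table, related Grade 3 fever or vomiting, which does not end dosing, does get prompt review. The required trial-level response is therefore slower for the graver event, and the protocol gives no reason for that order.

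What is at stake is the speed and certainty of escalation. Section 4.8 states that MVA/HIV62B and AIDSVAX B/E have not previously been given together in humans, so early notice of a severe reaction has some value. No endpoint, analysis or sample size is affected.

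**Working it through.** **Grade by grade.** For a related, non-serious reaction:

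| Reaction | Section 7.3.3 (individual) | Table 11-1 (trial) |
|---|---|---|
| Grade 3 subjective symptom on the footnote's list | Dosing continues | Exempt |
| Grade 3 fever or vomiting | Dosing continues | Immediate email, prompt review |
| Grade 4 subjective symptom on the footnote's list | Dosing stops permanently | Exempt |

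The rules agree in the first line. In the second, Table 11-1 is the stricter. In the third, Section 7.3.3 is the stricter. The second and third lines together make the inversion.

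**Scope.** Section 9.10.1 lists eight systemic symptoms. Footnote b names six of them, all but raised temperature and vomiting. It adds injection site pain and tenderness, so eight items are exempt.

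**What still covers an exempt Grade 4 event.**
- Section 9.10, as the usual rule: "a participant who self-reports any postvaccination reaction greater than mild is seen by a clinician within 48 hours after onset". Reactions that are getting better or are already over need no such visit.
- Section 11.2.1: safety forms are due "before the end of the next business day after receiving the information".
- Sections 2.5, 11.1.4 and 11.4.1: HVTN Core monitors daily. The latter two sections direct this at events that meet expedited-reporting, pause or prompt-review criteria. An exempt event is not a target, though its form may well be seen.
- Section 11.2.2: "Sites are expected to notify the Clinical safety specialist of any serious safety concern requiring their attention (Table 11-1". That sentence cites Table 11-1, so its reach to an exempted event is unclear. The same section gives a clinical safety phone for concerns needing immediate attention. The Clinical safety specialist sits on the PSRT (Section 11.1.1).
- Sections 9.4.1.1 and 9.4.1.4: fatigue, chills, myalgia and arthralgia can prompt a cardiac work-up. If myo/pericarditis is suspected, the specialist is told within 24 hours.
- Sections 11.3 and 11.4.2: PSRT discretion, and weekly PSRT review during the injection phase.

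None of these sets the PSRT a deadline with a pause as the default. Section 7.3.3 does not supply one either: it requires PSRT consultation after a type 1 hypersensitivity reaction, but not after a Grade 4 symptom.

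**Frequency.** The plan gives no figure for this event. The chance of at least one among n participants is 1 − (1 − p)^n. As a check, p = 1% and n = 40 gives 33.1%, as in Table 6-1. The rates p below are assumptions with no source in the documents.

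| Assumed p | At least one in 100 | At least one in 40 (Groups 2 and 4) | Expected in 100 (100 × p) |
|---|---|---|---|
| 0.1% | 9.5% | 3.9% | 0.1 |
| 0.5% | 39.4% | 18.2% | 0.5 |
| 1% | 63.4% | 33.1% | 1.0 |

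The severe systemic rates in the background do not fix p, because they are not Grade 4 rates. In HVTN 205 there were 4 such participants: 4/225 = 1.8% of those in the two vaccine regimens, or 4/213 = 1.9% of MVA recipients (Table 4-4). That count may include fever, which footnote b does not exempt. In HVTN 097 the figures were 4/80 = 5% on vaccine and 1/20 = 5% on placebo.

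**Timing.** These are upper limits on assumed clock times, with no holiday.
- Prompt route: a Monday 09:00 report plus 72 hours ends Thursday 09:00, 3.0 days. For a Friday 18:00 report, notice by Monday 09:00 plus 72 hours also ends Thursday 09:00, 5.6 days. At that limit the review is complete or the trial pauses.
- Exempt route: a form by Tuesday 17:00 plus a 7-day cycle gives 8.3 days from Monday 09:00. A form by Monday 17:00 plus 7 days gives 10.0 days from Friday 18:00. At that limit nothing happens by default.

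**The case against.** The best defence is that the two rules have different purposes. Not every event that stops one person need convene the PSRT: pregnancy also ends dosing permanently and is absent from Table 11-1. This stands as far as it goes, and it is why a reader who infers a contradiction between Sections 7.3.3 and 11.3 goes too far. A site can follow both rules at once. But pregnancy is not a reaction to the product. The separation of purposes does not explain why a related Grade 3 vomiting should escalate faster than a related Grade 4 headache.

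Second, the gap may be nearly empty. If most Grade 4 subjective symptoms also qualify as SAEs, the first row of the table already pauses the trial. The grading table and the expedited-reporting manual that would settle this are cited but not supplied. This stands in full and limits the point to an unknown number of non-serious events.

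Third, a reader might infer that these events go unreviewed, or that HVTN Core would not see them. The documents do not support that. The participant's dosing stops, forms arrive quickly, Core monitors daily, the PSRT looks weekly and may suspend dosing at any time. What is missing is a required prompt PSRT response with a default.

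Fourth, the background is reassuring. AIDSVAX B/E was given with another poxvirus vaccine in RV144 and HVTN 097, and in HVTN 097 severe systemic symptoms were equally frequent on vaccine and placebo, on small numbers. This also stands.

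**Conclusion.** The point holds as a minor misalignment between two rules that do not contradict each other. The textual finding is firm: footnote b has no grade limit, and the exception in Section 7.3.3 applies at Grade 3 only. The consequence is a slower required trial-level response for related, non-serious Grade 4 subjective symptoms, and for nothing else.

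Its practical size cannot be determined from the documents. The probabilities above illustrate assumed rates. It would be wrong to read 63.4%, or any other entry, as the trial's risk of such an event. The timing limits rest on assumed clock times and a worst-case weekly cycle. The gain from a change lies mainly in the immediate notice and the default pause, and less in the days saved.

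**What to change.** Open footnote b with the words *At Grade 3,* and leave its list as it is. Any related Grade 4 reactogenicity symptom would then trigger immediate email and prompt PSRT review, in line with the Grade 4 stopping rule in Section 7.3.3. Leave Grade 3 fever and vomiting under prompt review, as now. If the Grade 4 exemption is deliberate, say so and give the reason.

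The change is a few words, by one of the routes in Section 13 (a clarification memo or letter of amendment). The burden is a rare extra prompt review: 0.1 to 1 expected in the whole trial over the assumed range, at one review per event. There is a further, rarer cost. A review not completed in 72 hours would pause the trial, which holds all enrollment and vaccination (Section 11.3). A dose whose visit window closes in the meantime cannot be given (Section 7.3.2). With two doses per participant and recruitment limited to former HVTN 205 vaccinees, that is worth knowing, but it does not outweigh the change.
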